The proposed study will first investigate how short-term supplementation with GP-SPI may modify the gut microbial community in healthy participants while monitoring liver and kidney function/health. We will also perform a longitudinal, microbiome-wide association study (MWAS) to identify gut bacteria species/strains that are positively or negatively associated with GP-SPI supplementation. Metabolomics analysis will be performed on collected urine and blood samples to identify/quantify known and unknown metabolites. Shotgun metagenomic sequencing will be performed on fecal samples to generate high quality draft genomes for species/strain level identification. These dynamic data sets will serve as input for the MWAS to correlate increasing/decreasing levels of gut bacterial species/strains to increasing/decreasing metabolites in blood and urine. These bacteria-metabolite associations will then be used to infer cause-effect relationships that can be further tested *in vitro*. We expect that successful completion of these studies will contribute to mechanistic explanations for how dietary polyphenols such as grape PACs alter the gut microbiota and resulting MM to promote metabolic health.

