1.3 Research Design and Methods

Overview

This is a pilot time course study to characterize the effect of GP-SPI on the gut (i.e. fecal) bacterial community of healthy subjects. Following screening, enrolled subjects will washout of PAC-rich foods for 5 days while also consuming SPI. Subjects will then consume GP-SPI over a 10-day supplementation period. Fecal, urine, and blood samples will be collected. Comprehensive metabolic panel (CMP) tests performed before and after the GP-SPI supplementation period will monitor liver and kidney health. Using deidentified fecal, urine, and blood samples collected from time course study a MWAS study (funded by R01 AT010242-01) will be performed.

Successful completion of this pilot study will yield data that will inform the design of a follow-up placebo-controlled intervention study, which will be described in a separate clinical protocol that will be submitted to IRB for approval.

A. Research Procedures

[figure not shown]

Figure 1. Clinical Study Design

Location

Screening and out-patient visits will take place in the Surgery Clinic in the Clinical Academic Building (CAB) or Surgery Department (MEB 5) and NJ Institute of Food Nutrition and Health (IFNH).

Recruitment

Prospective participants will be recruited through flyers posted locally on Rutgers University campuses and sent to university email lists (**Flyer** attached). Interested subjects will call in or email to receive further information about the study. A member of the study team will give a brief summary of the study. If the subject requests a screening appointment, the investigator will ask for verbal consent to proceed with a list

of questions (**Telephone Script** attached). Collecting this information at this time assists in expediting the paperwork during the visit and spares ineligible subjects the inconvenience of a futile appointment.

Eligibility Screening

At the screening visit (at IFNH), a member of the study team will explain the study in detail to the subject. Full explanation of study procedures and potential risks will be provided. The subject will have ample time to read the Consent and ask questions before signing and proceeding with screening procedures. A signed copy of Consent form (form attached) will be given to the subject.

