After consent a participant ID will be assigned to subject. Demographics, medical history, height, and weight (**Demographics** and **Medical History** forms attached) will be recorded for each subject. Females will be given a urine-based pregnancy test onsite and result will be recorded. If inclusion criteria are met at this time, subject will be asked to schedule a visit at CAB with study nurses for a blood draw to perform CMP screening test. If CMP results are within normal range the subject will be enrolled and return to IFNH to receive study materials needed for participation in the study. If any CMP values are outside normal ranges subject will be advised that they do not fulfill all eligibility criteria, they will be given a copy of their CMP results, and if necessary, advised to see their primary care provider. All screened subjects will be documented on **Screening and Enrollment Log** (attached).

The final selection will be contingent upon the individuals meeting all eligibility criteria and deemed capable of complying with the study protocol.

Study Procedures

- Thirty subjects will be enrolled.
- **Food List:** Participants will maintain their usual diet except for a provided list of PAC-rich foods that they will be asked to abstain from for a 5-day wash-out period and during the 10-day intervention. The Food List is provided below. The goal is to have GP-SPI as the main/only source of PAC in the diet for the study period.
- **Wash-out and SPI (Day -5 through -1):** On day -5 (pre-baseline) before any supplementation, each subject will collect their fecal and urine sample. Each subject will then consume SPI twice a day (provided as pre-weighed packets of 20 g) during a 5-day wash-out period (days -5, -4, -3, -2, and -1). Subjects will be instructed to mix each packet of SPI in 250 mL of water or in a smoothie (recipe example below will be provided) using allowed foods as detailed in instructions and consume once in the morning before breakfast and once in the evening before dinner.

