4) Statistical analysis: To find the bacteria that respond to GP either positively or negatively (i.e. GP responders) we will omit those strains that are found to change with only SPI supplementation. To further understand how the GP responders affect host metabolic health as a group, we will derive a GP Responder

Index (GRI) based on the abundance and diversity [Heip evenness] of the identified bacteria (36). Data will be subject to two-way repeated measures ANOVA to decipher main effects and interactions between GP and SPI. $P < 0.05$ will be considered significant.

To detect significant differences in metabolites MetaboAnalyst 3.0 software (<http://www.metaboanalyst.ca/>) will be used. Principal components analysis (PCA) will transform original data variables into a smaller number orthogonal variables built from linear combinations to explain most of the data variance and cluster samples from each time-point or group to be analyzed. Significant difference ($p < 0.05$) will be determined within subject at different time-points, within group, and between groups. Variable importance in projection (VIP) scores will be estimated to select metabolites biomarkers from a partial least squares-discriminant analysis (PLS-DA). VIP scores are a weighted sum of PLS weights for each variable and measure the contribution of each predictor variable to the PLS-DA model. Compounds with VIP score > 4 represent metabolites with greatest change, which will be chosen for proof of identity. Before carrying out PCA and PLS-DA analyses, peak intensity will be controlled by a logarithmic transformation, and monitored by Pareto scaling. Methods for data preprocessing and statistical analysis will be optimized and additional corrections and tools will be applied as needed (37; 38).

Co-inertia analysis: To aid interpretation of the relationship between the bacterial responders and metabolomics datasets, they will be integrated using a multivariate method known as co-inertia analysis (CIA) (39). We expect to uncover bacterial species/strain level increases and decreases in GP-SPI-supplemented subjects that correlate with a concomitant increase and decrease in production of their metabolites.

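### With every participant on one SPI-then-GP-SPI schedule and no adjustment for study day, bacteria-metabolite associations may reflect shared GP-SPI exposure and should not carry cause-effect inference

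*Combined protocol and SAP*

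**What the plan says.** The overview in section 1.3 describes the design: "This is a pilot time course study to characterize the effect of GP-SPI on the gut (i.e. fecal) bacterial community of healthy subjects". A concurrent control is left to a later trial, which this pilot is meant to serve by yielding data to "inform the design of a follow-up placebo-controlled intervention study". All participants follow one timetable. First, "enrolled subjects will washout of PAC-rich foods for 5 days while also consuming SPI"; day 0 is a break; "Subjects will then consume GP-SPI over a 10-day supplementation period". Stool and urine are both collected on days -5, 0, 2, 4, 6, 8 and 10 (Table 1), the first of these before any supplement: "On day -5 (pre-baseline) before any supplementation, each subject will collect their fecal and urine sample". Serum metabolomics uses days 0 and 11 only (section 1.8).

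The statistical part of the MWAS description in section 1.3 starts by selecting bacteria: "To find the bacteria that respond to GP either positively or negatively (i.e. GP responders". Strains that change on SPI alone are dropped. Co-inertia analysis then joins the selected responders to the metabolomics data. The expected result is bacterial "increases and decreases in GP-SPI-supplemented subjects that correlate with a concomitant increase and decrease in production of their metabolites", so the metabolites that move with the bacteria are described as the bacteria's own. Section 1.2 states the use of the result: "These bacteria-metabolite associations will then be used to infer cause-effect relationships that can be further tested" in vitro.

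Neither section mentions adjusting for study day or exposure, centring, or comparing individual participants' changes. Section 6.1 plans mixed models outcome by outcome; it does not cover associations between a bacterium and a metabolite.

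**The concern.** Exposure to GP-SPI is fully determined by study day and is the same for everyone. The bacteria entering the integration are there because they change under GP-SPI. Section 1.3 also looks for metabolites that rise after GP intake and takes forward those with the greatest change; grape-derived compounds rise simply because they are swallowed. A bacterium and a metabolite that each respond to the powder will move together across days, whether or not the bacterium produces the metabolite.

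The signal that bears more directly on production is whether participants whose strain rises more than average also show a larger metabolite rise. The plan does not isolate it. At stake is which pairs go forward to in vitro work, and whether the wording of section 1.2 can be defended. The primary endpoint, microbiota composition by 16S sequencing, is not affected.

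**Working it through.** **The plan's own figure.** Section 1.5 gives 16 subjects and 96.2% power for a rise in *A. muciniphila* from 0.1% to 0.4% with SD 0.5%, that is (0.4 - 0.1)/0.5 = 0.6 SD. The within-subject correlation is not given, so the power cannot be derived from the stated inputs alone. Under compound symmetry, correlations of 0.80 to 0.88 reach 96.2%, and 0.5 gives 37-61%. This point does not rest on that figure; only the 0.6 SD is borrowed from it.

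**Inputs.** From the documents: 30 enrolled and 20% lost (section 4.3), so 30 × 0.8 = 24 participants; seven paired stool and urine days; two-sided 0.05 (section 6.1). Assumed: participant SD 1, residual SD 1, a bacterium rising in a straight line from day 0 to day 10 by *b*, and a metabolite stepping up by *m* on GP-SPI days. The two are otherwise independent, so no link exists.

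**Expected correlation after removing participant means.** The bacterial profile over the seven days is 0, 0, 0.2, 0.4, 0.6, 0.8, 1; the metabolite profile is 0, 0, 1, 1, 1, 1, 1.

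- Sum of squares, bacterium: G = 2.2 - 3²/7 = 0.914
- Sum of squares, metabolite: S = 5 - 5²/7 = 1.429
- Cross-product: C = 3 - (3 × 5)/7 = 0.857
- Residual sum of squares per participant: 7 - 1 = 6
- r ≈ *bm*C / √[(6 + *b*²G)(6 + *m*²S)]

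For *b* = *m* = 1: 0.857/√(6.914 × 7.429) = 0.12. With df = 24 × 6 - 1 = 143, the critical |r| is 1.977/√(143 + 1.977²) = 0.163.

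| *b*, *m* (residual SD) | expected r | simulated share p<0.05, within participant | same, after also removing day means |
|---|---|---|---|
| 0, 0 | 0 | about 5% | about 5% |
| 0.6, 0.6 | 0.05 | about 9% | about 5% |
| 1, 1 | 0.12 | about 30% | about 5% |
| 1, 2 | 0.19 | about 64% | about 5% |
| 2, 3 | 0.38 | nearly 100% | about 5% |

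The first row shows that the excess in the third column comes from the shared exposure.

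**Sensitivity to scale and shape.** If 0.6 SD is read against the total SD, with a within-subject correlation of 0.5, the residual SD is √0.5 = 0.71 and the rise is 0.6/0.71 = 0.85 residual SD. This is why the shares below exceed the 9% above. Shares of unlinked pairs with p<0.05, n = 24, ranging from gradual rise to immediate step for urine:

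| Bacterium 0.6 SD with | correlation 0.5 | correlation 0.8 |
|---|---|---|
| urine metabolite 0.6 SD | 21-43% | 76-97% |
| urine metabolite 2 SD | 82-97% | 100% |
| serum metabolite 0.6 SD (one pre, one post) | 25% | 72% |
| serum metabolite 2 SD | 70% | 98% |

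After removing day means the rate is 4-7% throughout.

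**Pooling all samples and ignoring participant.** In the first set-up this gives 25%, 33% and 84% at 1/1, 1/2 and 2/3 SD, but already about 21% with no GP effect. Most of the first figure and much of the second is repeated-measures clustering, not treatment.

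**What centring can and cannot do.** If participants differ in a way that scales both responses (assumed SD 0.5 of the mean response), unlinked pairs still reach p<0.05 in about 7% to 46% of cases after centring, over 1/1 to 2/3 SD. A true link in which the metabolite follows each participant's own bacterial level (slope 0.3) is found 93% of the time after centring, but only 27% of the time with a single change-against-change comparison, as serum would need. If the link shows only in a rise that all participants share, centring removes it and detection falls to 5-6%.

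**The case against.** The case against has real weight. This is a pilot, the MWAS is not the primary endpoint, and the secondary endpoint in section 1.3 is only to collect and store samples for it. Section 1.2 sends the associations to in vitro testing. Other evidence on production is planned: profiling of PAC-active enzyme genes, functional annotation, and glycerol-preserved stool for culture. Co-inertia is a descriptive method with no pairwise p-value, and section 1.2 names no test for its correlation, so the simulated test is a stand-in. The metabolomics paragraph also leaves room for further corrections as needed.

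This lowers the priority and means the percentages illustrate the problem; they do not forecast the study's results. It does not remove the problem. The SPI-only filter covers strains alone and leaves the shared GP effect in place. The open-ended provision for corrections commits to nothing on this point. The text does not tie the enzyme profiling to the choice of pairs, and in vitro work can test only the pairs it is given.

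A reader might infer that every GP responder will correlate with every GP-raised metabolite. The documents do not support that: at 0.6 residual SD for both features the share is about 9%, and shares near 100% need large assumed effects or high within-subject correlation. Nor is exposure simply elapsed time, because days -5 and 0 are both free of GP-SPI.

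**Conclusion.** The concern holds in this form: as written, the plan cannot tell production of a metabolite from joint response to the same supplement, yet it assigns causal meaning to the association. The share of associations affected is unknown. Under the assumptions shown it runs from little above the nominal 5% for weak responders to nearly all pairs for strong ones, so the pairs most likely to attract attention are the most exposed. The result rests on assumed metabolite effects, variance split and response shape, none of which the documents give; the direction does not depend on them.

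A further tempting step is to let centred associations alone support cause and effect. That goes too far. Centring removes the common day effect, but not differences between participants in adherence or transit time, which are plausible with self-administered packets and the variation in stool consistency that section 1.3 itself discusses. It can also miss true producers when participants respond alike. The change is worth making before the MWAS is run; it is not a flaw in the primary analysis.

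**What to change.** In section 1.3, under the statistical analysis and co-inertia paragraphs, state that:

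- the bacteria-metabolite integration (co-inertia and any pairwise correlation) is also run on data centred within participant and within study day;
- significance comes from permuting whole participant series, so that each time course stays intact;
- for serum, each participant's bacterial change from day 0 to day 10 is correlated with the metabolite change from day 0 to day 11;
- associations on uncentred data are reported as co-response to GP-SPI.

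In section 1.2, replace the cause-effect wording with a statement that the pairs are candidates for in vitro testing, with more weight on those that persist after centring.

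The cost is one preprocessing step and a permutation test on data already planned, with no new samples or participants. The price is fewer supported links, low power for serum and wherever participants respond alike, and a remaining risk of confounding by participant-level differences. Centred pairs therefore remain candidates too.

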1.4 Preliminary Data

The proposed study is a logical follow up to animal studies, which showed that compared to control mice fed a high-fat diet (HFD) supplemented with SPI alone, mice fed an isocaloric HFD supplemented with GP-SPI exhibited greater resistance to weight gain, adiposity, and glucose intolerance (6). Compared to HFD control group, mice fed the HFD supplemented with GP-SPI had lower levels of bacteria-derived lipopolysaccharide (LPS; endotoxin) in circulation. LPS triggers well-characterized systemic inflammatory responses in humans and mice. Coincidentally, analyses of intestinal tissue of mice fed the GP-SPI supplemented HFD revealed: i) a decrease in inflammatory mediators (TNF α , IL-6, iNOS), ii) increased expression of the tight junction protein occludin, indicating improved intestinal barrier integrity, iii) increased expression of Fiaf, indicating reduced peripheral deposition of fatty acids, iv) lower Glut2 expression, suggesting decreased glucose absorption, and v) higher expression of proglucagon (6). Collectively, these data suggested that GP-SPI supplementation improves metabolic resilience in a gut stressed by HFD. Fecal and cecal samples collected from mice fed HFD supplemented with GP-SPI showed higher levels of the gut bacterium *Akkermansia muciniphila* and a lower Firmicutes/Bacteroidetes ratio (6). In other words, polyphenols extracted from Concord grape or cranberry fruits and used as supplements triggered dramatic shifts in the type of bacteria that live in the gut, referred to as the “gut microbiota”.

We recently showed that GP-SPI can induce the *A. muciniphila* bloom within 14 days, independent of dietary fat, and that PACs, the major constituent of GP, was sufficient to induce the bloom (14). We also found that in addition to promoting intestinal abundance of *A. muciniphila* in mice, GP-SPI induced changes in several genera (i.e. *Oscillibacter*, *Clostridium IV*, *Intestinimonas*, *Acetatifactor*, *Blautia*, *Gemella*, *Romboutsia*, *Weissella*) in a direction that may also contribute to intestinal health (14). While there are differences at the strain/species level, mouse and humans share 89% of bacterial genera (40). Compared to controls, mice fed HFD supplemented with GP-SPI, but not LFD supplemented with GP-SPI, showed improved oral glucose tolerance after 2 weeks (14).

A. muciniphila is a Gram-negative obligate anaerobe that colonizes the mucus layer covering the intestinal epithelium. *A. muciniphila* can metabolize mucin as its only source of carbon and nitrogen (41) and was shown to modulate mucosal gene expression pathways involved in basal metabolism and immune tolerance toward the gut microbiota (42). For these reasons, it is thought that the bacteria species *A. muciniphila* has beneficial effects on carbohydrate metabolism. Consistent with this, treatment of Type 2 diabetic patients with the commonly used drug, metformin, triggered an increase in *A. muciniphila* population (43; 44). Increases in *A. muciniphila* were similarly observed in pregnant women with normal weight gain as compared to those with excessive weight gain (44; 45), and in normal weight and post-gastric-bypass subjects (46; 47). Prebiotic (oligofructose) treatment of *ob/ob* mice resulted in an improved metabolic profile (increased glucose tolerance, L-cell number, intestinal proglucagon gene expression and plasma GLP-1 levels alongside reduced adiposity, oxidative stress, and low-grade inflammation) concomitant with a ~100 fold increase in *A. muciniphila* compared to control *ob/ob* mice (48). Probiotic administration of *A. muciniphila* to HFD-fed mice reduced adiposity, metabolic endotoxemia, adipose inflammation and insulin resistance in association with increased intestinal levels of endocannabinoids that control inflammation, the gut barrier, and gut peptide secretion (49). Significantly, although it represents only 1 - 4 % of the gut microbiota in healthy subjects, the presence of *A. muciniphila* in the gut is inversely related to intestinal bowel disease (IBD), Crohn's disease, ulcerative colitis and appendicitis, suggesting its utility as a biomarker of intestinal health (41). A recent intervention study of sweetened dried cranberries, which are rich in PACs, observed a trend towards increased *Akkermansia* species after 2 weeks compared to baseline (50).

1.5 Sample Size Justification

Using conservative estimates for mean relative abundance (RA) of *A. muciniphila* in human subjects (i.e. baseline mean RA of 0.1% increasing to 0.4% on day 10 with standard deviation of 0.5%), a sample size of 16 subjects would be required to detect significant difference from baseline levels (target power = 95%, actual power = 96.2%; $\alpha = 0.05$, Hotelling-Lawley Trace test for repeated measures, GLIMMPSE).

16S rRNA gene sequencing data will be compared longitudinally within each subject and in aggregate and consists of surveying the relative composition of gut microbiota populations in fecal samples and mine data for differences in phyla (e.g. *Bacteroidetes* vs. *Firmicutes*), genera, and specific microbes (*Akkermansia* spp.) as far as resolution allows. Power calculations will be performed using data obtained from this pilot time course study to assist in finalizing design of a future randomized, placebo-controlled intervention study.

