4.3 Number of Subjects

A. Total Number of Subjects

30 subjects will be enrolled after successfully passing screening. The anticipated lost to follow-up rate for this study will be 20% (i.e. 6 non-completers)

B. Total Number of Subjects If Multicenter Study

N/A

C. Feasibility

We expect to recruit the majority of our participants from the New Brunswick campus of Rutgers University. With a relatively flexible study schedule and no particularly stringent eligibility criteria, we do not anticipate difficulties in engaging interest and accommodating schedules of participants. We conservatively expect a recruitment rate of 3-6 participants per month over 6 months.

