6.0 Data Management Plan

6.1 Data Analysis

Statistical comparisons will focus on individual and aggregate comparisons with respect to baseline to follow-up change in gut microbiota populations and biochemistry profile in blood and urine samples.

For each outcome, the equality of the outcome means for GP-SPI versus SPI will be tested against a two-directional alternative, controlling the type 1 error at $\alpha = 0.05$. The analyses will be conducted using t-tests for between group analysis and with repeated measures to conduct analysis of variance. Post-hoc tests will be conducted for pairwise comparisons of GP-SPI and SPI employing the Tukey method for controlling the global comparison-wise significance at 0.05 level. Logarithms or other transformations will be applied for data seriously deviating from normality; alternatively, non-parametric analyses may be conducted.

Handling of missing data: The data will be analyzed using the procedures PROC MIXED and PROC GLIMMIX SAS (v 9.3 or later). Thus, mixed effects models for repeated measures will be employed to analyze all available data irrespective of missing or incomplete data attributable to dropouts or other phenomena. In anticipation of the possibility of missing data, we plan to conduct sensitivity analyses that compare our findings against protocol completer analyses and last observation carried forward analyses in addition to investigating characteristics of participants who fail to protocol.

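### Does the 96.2% power need redoing because section 6.1 may move Akkermansia off the raw scale without fixing how?

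*Combined protocol and SAP*

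**What the plan says.** Section 1.5 gives the only power calculation in the protocol. Its inputs are "baseline mean RA of 0.1% increasing to 0.4% on day 10 with standard deviation of 0.5%), a sample size of 16 subjects", for a target of 95% and an attained 96.2%, using the "Hotelling-Lawley Trace test for repeated measures, GLIMMPSE". It does not state the within-subject correlation, the time points entered, or whether the one SD holds at every time.

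Section 6.1 plans t-tests, repeated-measures analysis of variance and mixed models (PROC MIXED, PROC GLIMMIX), two-sided at 0.05. For non-normal outcomes it says: "Logarithms or other transformations will be applied for data seriously deviating from normality; alternatively, non-parametric analyses may be conducted". It sets no threshold, names no rank test and says nothing about zero abundance.

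Section 4.3 enrols 30 and expects losses: "The anticipated lost to follow-up rate for this study will be 20% (i.e. 6 non-completers"), which leaves 24 completers. Section 1.5 also looks ahead: "Power calculations will be performed using data obtained from this pilot time course study to assist in finalizing design" of a later randomized trial.

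**The concern.** The power figure belongs to one analysis, and another will probably be run. If the SD of 0.5% applies at baseline, raw abundance cannot be close to normal, and the clause in section 6.1 comes into play. The analyst could then choose between logs, another transformation and a rank test after seeing the data.

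Two things would be at stake. First, 96.2% would not describe the test on which the Akkermansia hypothesis is judged, and Akkermansia is the only organism that the hypothesis names. Second, choosing the scale afterwards can change significance, inflate false positives, and leave it unclear which effect size goes into planning the follow-up trial.

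**Working it through.** **Inputs from the documents.** Means 0.1% and 0.4%, SD 0.5%, n = 16, alpha 0.05 (section 1.5); two-sided testing (section 6.1); stool samples on seven days: -5, 0, 2, 4, 6, 8 and 10 (section 1.3); 30 × 0.8 = 24 completers (section 4.3). **Assumed, because not stated:** the within-subject correlation ρ, equal across days; the mean profile over time; and, for steps 2 to 4, lognormal data.

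**1. Can 96.2% be reproduced?** With equal correlations, the Hotelling-Lawley test of any change over p days has noncentrality λ = n·Σ(μᵢ − μ̄)² / [SD²(1 − ρ)], on p − 1 and n − p + 1 degrees of freedom.

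- Two days: Σ(μᵢ − μ̄)² = 0.3²/2 = 0.045. At ρ = 0.82, λ = 16 × 0.045 / (0.25 × 0.18) = 16, and power is 96.2%. At ρ = 0.5, λ = 5.76 and power is 61.2%.
- Seven days, two at 0.1 and five at 0.4: the sum is (2 × 5/7) × 0.09 = 0.1286. At ρ = 0.8, λ = 16 × 0.1286 / (0.25 × 0.2) = 41.1, and power is 96.4%.
- Six days with a step after day 0: 94.7% at ρ = 0.85 and 99.4% at ρ = 0.9.

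The figure is attainable with an unstated correlation of roughly 0.8 to 0.9. In a two-day reading, lognormal data with these means and SDs cannot have a raw correlation above (exp(1.805 × 0.970) − 1)/√(25 × 1.5625) = 0.76, which gives about 90%. That limit depends on both the two-day reading and the lognormal form, so it does not show an error.

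**2. Is the raw scale likely to be abandoned?** A normal model with mean 0.1 and SD 0.5 puts Φ(−0.2) = 42% of baseline values below zero. The analysis uses within-subject changes, so those are what need checking. With lognormal data and 24 participants, a Shapiro-Wilk test rejects normal changes in 89–93% of trials. If 0.5% is only the day-10 SD and the baseline SD is 0.125% (the same ratio of SD to mean, an assumption), it still rejects in about 88–96%. So yes, the clause would probably be used.

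**3. What does that do to power?** The log-scale SDs are √ln(1 + 5²) = 1.805 and √ln(1 + 1.25²) = 0.970. The medians are 0.0196% and 0.250%, a log difference of ln(12.7) = 2.545. At log-scale correlation 0.3 the SD of the log change is √(3.258 + 0.941 − 2 × 0.3 × 1.805 × 0.970) = 1.774. The noncentrality is then 2.545/1.774 × √24 = 7.0 against a critical value of 2.07, so power is about 100%. Simulated results for day 10 versus day 0, n = 24, log-scale correlation 0.3 to 0.8:

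| Case | Raw t | Log t | Raw and log disagree |
|---|---|---|---|
| SD 0.5% on both days | 87–96% | about 100% | 4–13% |
| Baseline SD 0.125% (assumed) | 97–99% | about 100% | 1–3% |

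With SD 0.5% on both days the signed-rank test exceeds 99%. In that case, setting values below 0.005–0.01% to zero and varying the added constant from 0.01% to 0.0001% changes significance in no trials.

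**4. What does a free choice of scale cost?** With no effect, the raw test rejects in 2% of trials, the log test in 5%, and either one in about 6%. Adding the signed-rank test gives about 8%. Adding a square root, shifted logs and a sign test gives about 9–9.5%. Logs used only when a normality test rejects give 4–5%.

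**The case for a change.** The best case for a change is that one sentence fixing the scale and the zero rule costs almost nothing, and that a day-10 SD above 0.5% is plausible. If GP-SPI multiplies every participant's abundance by four, the day-10 SD would be 2.0% (an assumption, not in the documents). On the same two-day comparison raw power falls to 32–58%, and raw and log disagree in 42–57% of trials. If 30% of participants also carry no Akkermansia (assumed), log power is about 72–74% at correlation 0.3, and the treatment of zeros begins to matter.

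This shows that the raw scale can be a poor choice. It does not show that the plan goes wrong: in the fourfold case a normality check rejects in about 99% of trials, section 6.1 then points to logs, and the log test keeps 86% to over 99% power when everyone carries the organism. The weaker figures require two assumptions beyond the documents.

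A second argument is that the metabolite analysis fixes its scale: "peak intensity will be controlled by a logarithmic transformation, and monitored by Pareto scaling". But that step is stated for the principal-component and discriminant analyses, and the same section leaves preprocessing open to optimisation, so the contrast is slight.

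The third argument concerns the follow-up trial: under lognormality the stated values mean a fourfold rise in means but a 12.7-fold rise in medians. That is a reason to state the scale when the pilot is summarised. The pilot data can be summarised on either scale at that point.

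What stands is that section 6.1 lacks a criterion, a named rank test and a zero rule, and that the inputs behind 96.2% are incompletely reported.

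**Conclusion.** The observation is accurate but calls for no change; it is missing detail of a kind that analysts fill sensibly. The 96.2% is a raw-scale, normal-theory figure. It is attainable and not shown to be wrong. The likely departure from it, a log analysis, is one that section 6.1 already provides for. With the stated SD that departure raises power from 87–96% to about 100% at 24 completers, and the number required was only 16. The price of the open wording is about 6% false positives if the better of raw and log is reported, and up to roughly 9.5% only if a wide menu of tests is searched.

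These sizes rest on lognormal data, log-scale correlations of 0.3 to 0.8, a day 10 versus day 0 comparison standing in for the mixed model, and the protocol's SD of 0.5%. A much larger day-10 spread combined with many non-carriers would lower power, but the documents give no figure for either. For a single-arm pilot whose primary endpoint is overall microbiota composition, the sample size and the validity of the analysis are not in doubt on this ground.
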